# 4.2 Exclusion Criteria, Step 1: Entry for Cohort 1, Cohort 2a, and Cohort 2b

Potential participants must be excluded from the study if any of the conditions specified below are identified during the screening period (i.e., within 28 days prior to study entry). The screening period begins when parental permission and informed assent (if applicable) are obtained and ends immediately prior to enrollment. For criteria involving a potential participant's medical history, it is expected that each exclusionary condition will be assessed at screening and subsequently reviewed and confirmed on the day of study entry, prior to enrollment. In these criteria, "at entry" is used to refer to the day of enrollment in the study.

- **4.2.1** Within 6 months prior to entry, any HIV-1 RNA value >400 copies/mL OR two consecutive "viral blips," defined as an HIV-1 RNA value ≥50 copies/mL but ≤400 copies/mL.
- **4.2.2** As determined by the IoR or designee, and based on available medical records, known or suspected resistance to NNRTIs.
  - *Note:* Prior receipt of NNRTIs for prophylaxis or treatment is not exclusionary.
- **4.2.3** As determined by the IoR or designee, and based on available medical records, known or suspected resistance to INSTIs.
- **4.2.4** Ongoing congestive heart failure, symptomatic arrhythmia, or any current clinically significant cardiac disease, as determined by the IoR or designee, and based on available medical records.

- **4.2.5** Has any of the following, as determined by the IoR or designee based on participant/parent/guardian report and available medical records:
  - **4.2.5.1** Current hepatitis C infection
  - **4.2.5.2** Current clinically significant hepatic disease
  - **4.2.5.3** Current or anticipated need for chronic anti-coagulation
  - **4.2.5.4** History of known or suspected bleeding disorder, including a history of prolonged bleeding
  - **4.2.5.5** History of sensitivity to heparin or heparin-induced thrombocytopenia, as determined by the IoR or designee, based on available medical records
  - **4.2.5.6** Risk factors for Torsade de Pointes (e.g., heart failure, hypokalemia, hypomagnesemia)
  - **4.2.5.7** Known or suspected allergy to study product components.
  - **4.2.5.8** Known phobia to needles
- **4.2.6** More than one seizure within one year (defined as within 365 days) prior to entry, or unstable or poorly controlled seizure disorder, as determined by the IoR or designee, and based on available medical records.
- **4.2.7** Has the following combination of laboratory test results at screening (i.e., from specimens collected within 28 days prior to entry): ALT greater than or equal to 3 x ULN and total bilirubin greater than or equal to 1.5 x ULN and direct bilirubin greater than 35% of total bilirubin.
- **4.2.8** At entry, known active tuberculosis infection, as determined by the IoR or designee based on participant/parent/guardian report and available medical records.
- **4.2.9** At entry, any ongoing pancreatitis as determined by the IoR or designee based on participant/parent/guardian report and available medical records.
- **4.2.10** At entry, has symptoms suggestive of active coronavirus disease 2019 (COVID-19) or test results or contacts that require quarantine per local clinical practice, public health, and/or infection control guidelines as determined by the IoR or designee based on participant/parent/guardian report and available medical records.

*Note:* Potential participants with symptoms suggestive of active COVID-19, test results, and/or contacts that require quarantine may resume screening (or be re-screened) after symptoms have resolved and applicable quarantine requirements have been completed.

**4.2.11** Receipt of any prohibited medication within 7 days prior to entry, with the exception of antiviral agents that are part of the participant's ART regimen, as determined by the site investigator based on participant/parent/guardian report and available medical records, see Section 5.7.

*Note:* Medications and vaccines approved for emergency use (e.g., COVID vaccines) that do not appear in the IMPAACT 2036 Prohibited and Precautionary Medications listing are not exclusionary may be administered as per standard of care.

**4.2.12** Any past or current exposure to CAB LA or RPV LA

- **4.2.13** At entry, based on physical examination, has a current inflammatory skin condition that compromises the safety of intramuscular injections, as determined by the IoR or designee.
- **4.2.14** At entry, based on physical examination, has a dermatological condition overlying the buttock or upper thigh region, which, in the IoR or designee's opinion, may interfere with the interpretation of injection site reactions.
- **4.2.15** Enrolled in another clinical trial of an investigational agent, device, or vaccine.
- **4.2.16** Has any documented or suspected clinically significant medical or psychiatric condition or any other condition or social circumstance that, in the opinion of the site investigator, would make participation unsafe, complicate interpretation of study outcome data, or otherwise interfere with achieving the study objectives.

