#### Administration

Regardless of formulation, the first doses of oral CAB + RPV will be administered in the clinic at the Entry visit for Cohort 1 and Cohort 2a and must be directly observed by study staff. At the Week 2, Week 4a, and Week 4b (if indicated) study visits, the oral study product dose must also be administered and/or witnessed by clinic staff. If desired, the observed doses during these visits can be prepared and/or administered by the participant (or caregivers, as applicable) as part of the study product adherence assessment process.

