#### **Precautionary and Prohibited Concomitant Medications**

For a list of medications that should be used with caution and prohibited medications while on study product, refer to Appendix III.

Any study participant who requires a medication considered prohibited while on study product must have the study product held or permanently discontinued. Upon identification of the need for a prohibited medication, the site investigator should consult the CMC for further guidance on determining next steps for clinical management, study product management, and per Section 8.4.

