#### 6.4 Cohort 2b

# 6.4.1 Entry Visit: Cohort 2b (straight to injection)

The Cohort 2b Entry visit must occur within 28 days (inclusive) from the Screening Visit and may not be split over multiple days (with the exception of the 24-hour post-dose PK sample, which will be collected the day after Entry). Entry visit procedures that may provide information relevant to eligibility for the study should be performed first, prior to final eligibility determination and enrollment. In the event a participant is found to be ineligible on the day of enrollment, enrollment should not occur.

The following visit procedures must be conducted during the Entry Visit in the sequence specified below:

• Complete final eligibility determination and confirmation (medical and medications history including ARV history assessment, targeted physical exam, and a pregnancy test for participants

\*If indicated

^ For participants of childbearing potential.

of childbearing potential defined as having reached menarche or assigned female sex at birth and engaging in sexual activity that could lead to pregnancy.)

- Complete a paper-based Step 1 eligibility checklist
- Enroll the participant and obtain SID
- Provide adherence counseling to confirm the participant/parent/guardian is willing for the participant to receive injectable study product.
- Prescribe injectable study product
- The pre-dose PK sample must be collected prior to the participant's first study product injection.
- Administer the injectable study product
- Collect the post-dose PK samples at the specified timepoints

In addition, specimens for all laboratory evaluations at the Entry visit should be collected prior to the first injection, with the exception of the post-dose PK sample collections. The 24-hours post-dose PK sample will be collected on the day following the Cohort 2b Entry visit. Height and weight must again be collected with the 24-hours post-dose PK sample collection. Note that acceptability and tolerability assessments should be administered relative to other Entry visit procedures as specified in the IMPAACT 2036 MOP. Parents/caregivers are generally expected to be enrolled to the study at the participant's Entry visit; see Section 6.14 for additional details regarding the acceptability and tolerability assessments.

Cohort 2b	Entry Visit Proced	ures
Administrative		Complete final eligibility determination and confirmation*

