## 10.3 Pharmacology Study Design, Modeling, and Analysis

Oral and LA regimens with the proposed initial doses in this pediatric population are expected to achieve plasma concentrations within an acceptable range of those observed clinically in adolescents and adults. Initial doses selected for each weight band, based on prior data and modeling, are described in Section 5.

Pharmacokinetic blood samples will be collected as noted in Section 6 and Appendix I. Of note, PK samples need to be protected from light from sampling through analysis as detailed in the LPC.

Cohort 1 (with oral lead-in): Plasma concentrations for both CAB and RPV will be measured in at least the first 8 participants across Weight Bands 1 and 2, and at least the first 8 participants across Weight Bands 3, 4, and 5 according to the Rich Sampling Schedule as follows:

- Oral dosing
  - O Wk. 2: Pre-dose, 1, 2, 3, 4 and 8h post dose (6 samples)
- Long-acting injectable dosing:
  - o Wk. 4b: Pre-dose and 2h and 24h post dose,
  - o Wk. 5: Day 2-7 post-dose,
  - o Wk. 6: Day 12-16 post-dose,
  - o Wk. 8: pre-dose,
  - o Wk. 9: Day 3-7 post-dose,
  - Pre-dose prior to injections at Wk. 12, Wk. 16, Wk. 24, Wk. 32, Wk. 40, Wk. 48, Wk, 56, Wk. 64, Wk. 72.

Cohort 1 (with oral lead-in) and Cohort 2a (with oral lead-in): Once the proposed dosing regimens have been evaluated in each weight band and data are sufficient for the PK parameter estimates for both oral and IM dosing, then the Limited Sampling Schedule (below) will be used for the remainder of participants (through Week 72 for Cohort 1 and Week 48 only for Cohort 2a). Operational guidance for implementing the Limited Sampling Schedule for newly enrolling and currently enrolled participants will be provided in the IMPAACT 2036 MOP with additional communication provided to site teams at the time of implementation in a Memorandum of Operational Instruction.

- Oral dosing
  - o Wk. 2: Pre-dose and 3h post dose (2 samples)
- Long-acting injectable dosing:
  - o Wk. 4b: Pre-dose and 2h post dose
  - o Wk. 5: Day 2-7 post-dose,
  - o Pre-dose prior to injections at Wk. 8, Wk. 16, Wk. 24, Wk. 32, Wk. 40, Wk. 48, Wk56, Wk. 64, Wk. 72.

Cohort 2b (straight to IM dosing): For participants who do not receive oral doses, and start with IM dosing at Entry, the following IM-only Sampling Schedule will be used:

- Long-acting injectable dosing:
  - o Entry: Pre-dose and 2h and 24h post dose,
  - o Day 3: Day 2-7 post-dose,

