## **Appendix III-B: Prohibited Medications**

The below section contains listings of prohibited medications for **specified participants** at **specified timepoints during study participation** and **within 7 days prior to entry (per exclusion criterion 4.2.11)**. If, for any of the below medications, the participant cannot discontinue or change to an allowable alternative, refer to protocol Section 8.5 for participant management due to prohibited medications.

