## Additional Prohibited Medications During Oral Lead-In (Step 1 Participants) or Oral Bridging (Step 2 Participants):

In addition, participants must discontinue the following (or change to an allowable alternative) while receiving oral RPV study product as part of the Step 1 regimen of oral CAB + oral RPV:

• Proton pump inhibitors, such as esomeprazole, lansoprazole, omeprazole, pantoprazole, rabeprazole

Additional Prohibited Medications While Receiving Injectables (Step 2 Participants)

For participants receiving CAB LA and RPV LA, use of anticoagulation agents for greater than 14 days is prohibited, with the exception of the use of anticoagulation for DVT prophylaxis (e.g., postoperative DVT prophylaxis) or the use of low dose acetylsalicylic acid (325 mg). Systemic anticoagulation (including prophylaxis doses) on the day of an IM injection should be avoided.

Note: Any prohibited medications that decrease CAB or RPV concentrations should be discontinued for a minimum of 4 weeks or a minimum of three half-lives (whichever is longer), prior to the first dose and any other prohibited medications should be discontinued for a minimum of 2 weeks or a minimum of three half-lives (whichever is longer) prior to the first dose.

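### Exclusion 4.2.11 uses a 7-day look-back for prohibited drugs, but the Appendix III-B note asks for at least 4 or 2 weeks before a first dose that is given on entry day

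*Protocol*

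**What the plan says.** Two rules govern how long a child must have been off a prohibited drug.

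- **The 7-day rule.** Protocol 4.2.11 excludes "Receipt of any prohibited medication within 7 days prior to entry, with the exception of antiviral agents" that form part of the child's ART regimen. The introduction to Appendix III-B gives the same window: "within 7 days prior to entry (per exclusion criterion 4.2.11").
- **The longer rule.** The note at the end of Appendix III-B sets two washouts before the first dose, and in each the greater of the fixed period and the half-life period applies. For one class the note reads: "Any prohibited medications that decrease CAB or RPV concentrations should be discontinued for a minimum of 4 weeks or a minimum of three half-lives". The remaining drugs get a shorter fixed period: "any other prohibited medications should be discontinued for a minimum of 2 weeks or a minimum of three half-lives".

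The two are linked. 4.2.11 refers the site to Section 5.7, and Section 5.7 says "For a list of medications that should be used with caution and prohibited medications while on study product, refer to Appendix III". A site that follows the criterion therefore arrives at the note.

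The first dose falls on entry day throughout. For Cohorts 1 and 2a, Section 5.3.1 says the "first doses of oral CAB + RPV will be administered in the clinic at the Entry visit". For Cohort 2b, the Entry visit sequence in 6.4.1 includes "Administer the injectable study product", and Section 10.3 sets a sampling schedule "For participants who do not receive oral doses, and start with IM dosing at Entry".

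**The concern.** Both windows count back from the same day, and the protocol does not say which governs. Two sites could handle the same child differently, or one could record a deviation where the other records none.

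The class with the longest washout is the one that matters most. Appendix III-B warns that the enzyme inducers on its list (rifamycins, carbamazepine, phenytoin and others) can lower CAB and RPV markedly. Section 1.2.5.1 warns that sub-therapeutic levels of either long-acting drug can lead to virologic failure and resistance. Cohort 2b has no oral lead-in, so a depot that cannot be removed could be injected 8 days after an inducer, well inside the protocol's own minimum.

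**Working it through.** **Inputs.** 7 days (4.2.11 and III-B introduction); 4 weeks = 28 days and 2 weeks = 14 days (III-B note); visit windows from Appendix II; sampling days from Section 10.3. Entry is Day 0. I read the 7-day window as including Day -7, so the latest admissible last dose is Day -8.

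**Shortfall against the note on entry day**
- Drugs that lower CAB or RPV: 28 - 8 = 20 days. Last doses on Days -8 to -27 pass 4.2.11 and breach the note.
- Other prohibited drugs: 14 - 8 = 6 days. Last doses on Days -8 to -13 do the same.
- The three-half-lives clause exceeds 28 days when the half-life is over 28/3 = 9.3 days, and can only widen the gap.

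**If the note means the first injection**
- Cohorts 1 and 2a: Week 4a can be as early as Day 28 - 7 = 21, and Week 4b may be combined with it, so the first injection is at least 21 + 8 = 29 days after the last dose. With the four-week oral minimum in Section 3.1 it is 28 + 8 = 36. Both fixed minimums are met.
- Cohort 2b: the first injection is on Day 0, 8 days after the last dose. The 20-day shortfall remains.

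**Which samples fall within 28 days of a Day -8 last dose**

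| Cohort | Sample | Study day | Days since last dose |
|---|---|---|---|
| 2b | Entry, pre-dose to 24 h | 0 to 1 | 8 to 9 |
| 2b | Day 3 | 2 to 7 | 10 to 15 |
| 2b | Week 2 (Section 10.3) | 12 to 16 | 20 to 24 |
| 2b | Week 2 (Appendix II window) | 7 to 20 | 15 to 28 |
| 2b | Week 4 pre-dose | 21 to 31 | 29 to 39 |
| 2b | Week 8 trough criterion | 49 to 63 | 57 to 71 |
| 1, 2a | Week 2 oral PK | 7 to 20 | 15 to 28 |
| 1, 2a | Week 12, earliest | 21 + 56 - 7 = 70 | 78 |

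The Week 12 long-acting criterion and the Cohort 2b Week 8 trough criterion both lie well beyond 28 days. What falls inside is early Cohort 2b sampling and the Week 2 oral profile in Cohorts 1 and 2a.

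**Week 2 oral AUC, illustration only.** The protocol gives no rate at which induction wears off. Assume one of 8 children is affected, AUCs are log-normal, and the log-SD is 0.49 to 0.55, borrowed from the adult long-acting troughs in Table 12. In 1,000,000 simulated sets, the median falls on average by 1.3% if that child's AUC is 10% lower and by 3.9% if it is 30% lower. If that child is forced to be the lowest of the eight, the average fall is 7.7% to 8.5%. That is a mean and not a ceiling: about 40% of such sets fall by more than 8.5%, and 5% fall by more than 24% to 27%. The acceptance windows in Section 10.3.1 span 277/38 = 7.3-fold for CAB and 4166/1250 = 3.3-fold for RPV.

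**The case against.** The best defence is that 4.2.11 is the operative rule and the note is advice.

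- **Strength of wording.** Section 4.2 conditions are mandatory, the note only recommends, and the III-B introduction itself cites 4.2.11 for the entry window. A site can satisfy both rules by waiting longer. 4.2.16 and advice from the Clinical Management Committee could also stop an unsuitable child. This weakens the charge of impossibility, but not the conflict: the note states a minimum, the criterion admits children below it, and neither discretionary route tells a site which to follow.
- **The note cannot be literal.** The III-B list includes antiretrovirals not specified in the protocol. Stopping ART two weeks early would contradict the requirement for stable ART up to entry, and only 4.2.11 carries the ART exception. That stands, and it shows that the note needs correcting too.
- **Placement.** The note is printed under the heading for injectables. Read that way, the conflict shrinks to Cohort 2b, which may hold as few as 4 children and has no primary objective. It does not disappear.
- **Few children.** Known active tuberculosis (4.2.8) and poorly controlled seizure disorder (4.2.6) are exclusions, which removes many likely users of inducers. This stands and limits the importance.

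**Conclusion.** The inconsistency is real and concerns who may be dosed. On entry day the 7-day rule falls short of the note by up to 20 days for drugs that lower CAB or RPV and up to 6 days for other prohibited drugs, more where three half-lives is longer. On the narrowest reading it survives in Cohort 2b, where the consequence for an individual child is greatest.

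A reader might infer that the Week 12 gate for opening Weight Bands 4 and 5, or a primary estimate, is at risk. The documents do not support that: the Week 12 sample comes at least 78 days after the last permissible inducer dose, and the Cohort 2b Week 8 criterion at least 57. A reader might equally take the simulated Week 2 figures as a guarantee of no effect. They are averages under borrowed assumptions and bound nothing.

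The case rests on contradictory eligibility instructions and on protecting directly injected children. It assumes that Day -7 counts as excluded; if it does not, the shortfalls grow by one day. The change should be made, but it does not threaten the trial's conclusions.

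**What to change.** In 4.2.11 and the Appendix III-B introduction, replace 7 days with the note's windows, counted back from entry:

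- the longer of 28 days or three half-lives for the nine enzyme inducers listed in Appendix III-B under study treatment;
- the longer of 14 days or three half-lives for other prohibited drugs, applied only to those prohibited for that cohort's formulation.

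State the window for proton pump inhibitors explicitly. They matter only where oral RPV is given, so not at Cohort 2b entry. Section 1.2.2 says drugs that raise gastric pH can affect oral RPV exposure, so the team must decide whether they belong to the RPV-lowering class.

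In the note, define the first dose as the entry-day dose and carry over the ART exception from 4.2.11. Keep the separate 30-day consultation for topical imiquimod. Bring the eligibility checklist into line.

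**Cost.** Mainly wording. Table 3 already records all medications taken in the 28 days before enrollment, so the fixed minimums need no new data. A longer look-back is needed only for drugs with a half-life over 9.3 days. A few children will enrol later or use the one permitted re-screen.

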#### 4.3 Inclusion Criteria, Step 2: Continuation for Cohort 1 and Cohort 2a to injection phase

All participants enrolled in Cohort 1 or Cohort 2a will be assessed for eligibility to progress from the oral lead-in phase (Step 1) to the injection phase (Step 2), primarily based on the safety assessments from the Step 1 Week 4a study visit. Clinical assessments conducted prior to administering the first injection at the Week 4b visit will also be used to confirm eligibility to receive the injectable study product. See Sections 6.3.3 and 6.3.4 for Week 4a and Week 4b visit scheduling and order of procedures, respectively.

All of the following criteria must be met in order for a participant enrolled in Cohort 1 or Cohort 2a to be included in Step 2:

- **4.3.1** Currently enrolled as a participant in Step 1.
- **4.3.2** Has normal, Grade 1, or Grade 2 results from all of the following laboratory test results based upon specimens collected at the Week 4a study visit or from confirmatory repeat testing of Week 4a study visit laboratory tests:

```

# 4.4 Exclusion Criteria, Step 2: Continuation for Cohort 1 and Cohort 2a to injection phase

Participants in Cohort 1 or Cohort 2a who meet any of the following criteria will be excluded from Step 2:

- **4.4.1** Has permanently discontinued oral study product.
- **4.4.2** Occurrence of any grade 3 or higher adverse event assessed as related to study product during Step 1.
- **4.4.3** Any other condition or social circumstance situation that, in the opinion of the IoR or designee, would make continued study participation unsafe, complicate interpretation of study outcome data, or otherwise interfere with achieving the study objectives.

# 4.5 Inclusion Criteria for Parents/Caregivers

Parents/caregivers of participants will be considered for enrollment to complete quantitative behavioral surveys and/or qualitative in-depth interviews (IDIs), as indicated in the SoE. One parent/caregiver per participant should be enrolled to complete all behavioral assessments, including the IDI, when applicable. Informed consent for parent/caregiver enrollment should be obtained at the entry visit, after the child participant's eligibility has been confirmed, and may be completed at a later date, if necessary. However, parent/caregiver consent must occur prior to any study assessments being conducted. The enrolled caregiver may be the different than the parent or legal guardian who provided written permission for the child to participate. If, at any point the enrolled parent/caregiver for a given participant withdraws from the study or is unable to complete remaining study assessments for any reason, they may be replaced.

Caregivers must meet the following criteria to be eligible to enroll in IMPAACT 2036:

- **4.5.1** 18 years of age or older
- **4.5.2** Able and willing to provide written informed consent consistent with site IRB/EC policies and procedures
- **4.5.3** Caregiver, defined as a biological parent, legal guardian, or other person who provides significant emotional, psychological, and/or physical care to a child enrolled in IMPAACT 2036, based on self-report

